5.8.3 Individual Patient Discontinuation

All study participants have the right to voluntarily withdraw from the study at any time. In addition, the investigator has the right to discontinue a patient from the study at any time. Reasons for withdrawal from the study may include the following:

- Patient withdrawal of consent at any time
- Any medical condition that the investigator or sponsor determines may jeopardize the patient's safety if he or she continues in the study
- Investigator or sponsor determines it is in the best interest of the patient
- Non-compliance (e.g., frequently misses doses, visits)

Guidance for diagnosis and management of important potential class toxicities noted on HMPL-689 trials and/or those associated with other PI3K δ inhibitors is provided in [Section 6.8](#).

The primary reason and date for discontinuation must be recorded appropriately on the CRF.

In addition, stopping rules for individual patients during the dose escalation ([Section 5.8.3.1](#)) and dose expansion ([Section 5.8.3.2](#)) stages are outlined below.

5.8.3.1 Individual Patient Stopping Rules – Dose Escalation

For specific guidance on the diagnosis and management of important potential class toxicities associated with HMPL-689 and/or other PI3K δ inhibitors, please refer to [Section 6.8](#).

Dosing will stop for an individual subject, if any of the following occurs:

- A DLT that has not returned to Grade 1 (inclusive) or lower within 14 days, or a DLT that re-occurs in the same subject at a de-escalated lower dose level
- A DLT equivalent beyond Cycle 1 that has not resolved (even with medical intervention) within 14 days, or that reoccurs after the patient receives a de-escalated lower dose level

5.8.3.2 Individual Patient Stopping Rules – Dose Expansion

For specific guidance on the diagnosis and management of important potential class toxicities associated with HMPL-689 and/or other PI3K δ inhibitors, please refer to Section 6.8.

- An adverse drug reaction (ADR) severity and its resolution will determine dose interruption, reduction, or discontinuation for an individual
- ADR resolution will determine if subject will discontinue treatment altogether or at the discretion of attending physician, resume treatment at; i) the same dose level, or ii) at a lower dose
- If in professional opinion and recommendation of the PI, individual patients should withdraw from the study
- ADR emerging from drug-drug interaction or food-effect may lead to dose interruption, reduction, or discontinuation

5.8.4 Study Treatment Discontinuation

Patient must discontinue the study treatment in case of:

- Disease progression
- Intolerable toxicity
- Use of new antineoplastic therapy
- Pregnancy with onset during study

The primary reason for study treatment discontinuation should be recorded on the appropriate CRF. Discontinuation from HMPL-689 treatment does not mean discontinuation from the study, and the remaining study procedures should be completed as indicated in the study protocol.

In addition, stopping rules for a cohort or study during dose escalation (Section 5.8.4.1) and dose expansion (Section 5.8.4.2) stages are outlined below.

5.8.4.1 Cohort or Study Stopping Rules – Dose Escalation

There will be no escalation to the next cohort higher dose level until all available data from the current cohort dose level have been reviewed and analyzed by SRC, which will then recommend appropriate dose escalation, de-escalation, or discontinuation. This dose escalation stage will be suspended, interrupted, or discontinued before MTD is attained based on:

- recommendation of SRC
- analysis of emerging PK data, which suggests dose-exposure or target engagement is saturated

At the end of the DLT assessment window for a cohort dose level, safety data will be evaluated to determine either to escalate to the next cohort of higher dose level (Figure 1) or de-escalate to a specific lower dose level (not necessarily pre-specified). The need for dose escalation beyond 50 mg QD, de-escalation to below 5 mg QD, or other regimens, such as BID, will be evaluated and determined by the SRC based on all available cumulative data on safety, PK, pharmacodynamics, and efficacy.

Below are other scenarios that may be applicable:

- One out of 3 patients with DLT will lead to an increase in number of patients on that cohort dose level
- Three out of 6 patients with DLTs will lead to de-escalation to a lower level dose
- Three or more out of 6 patients with DLT at current dose indicate that the dose is unsafe, and that this dose should be de-escalated or discontinued.
- Six out of 6 patients with DLTs at cohort #1 (initial starting dose) may lead to termination of the study arm, amendment of the protocol to reflect a new lower starting dose or changes to inclusion/exclusion criteria, or termination of the entire study.

5.8.4.2 Cohort or Study Stopping Rules – Dose Expansion

The MTD/RP2D of expansion stage 2 will be the dose determined as safe by the SRC based on the conclusion of dose escalation stage 1 section of this phase 1 clinical trial.

The dose or any of the treatment arms/cohorts/tumor types may be re-evaluated for dose interruption, suspension, or reduction based on review of emerging safety data and recommendation of the safety committee.

CCI

5.8.5 Study and Site Discontinuation

This study may be temporarily suspended or prematurely terminated if there is sufficient reasonable cause. The sponsor will notify the investigator if the study is placed on hold, or if the sponsor decides to discontinue the study or close any site. If the study is prematurely terminated or suspended, the PI will promptly inform study participants and the Institutional Review Board/Independent Ethics Committee (IRB/IEC). Patients will be contacted, as applicable, and be informed of changes to study visit schedule. Reasons for suspension or termination the study include:

- Determination of unexpected, significant, or unacceptable risk to patients
- Demonstration of efficacy that would warrant stopping
- Insufficient compliance to protocol requirements
- Data that are not sufficiently complete and/or evaluable
- Determination that the primary endpoint has been met
- Determination of futility

The study may resume once concerns about safety, protocol compliance, and data quality are addressed, and satisfy the sponsor, IRB/IEC and/or participating regulatory authorities.

5.9 Pharmacokinetic, Pharmacodynamic, and Pharmacogenetic Assessment Methods

5.9.1 Pharmacokinetic Assay

Plasma samples will be analyzed to determine concentrations of HMPL-689 using a validated, specific, and sensitive liquid chromatography-tandem mass spectrometry method. If required, some plasma samples may be analyzed to document the presence of circulating metabolites using a qualified research method.

5.9.2 Collection Schedule for Pharmacokinetic Samples

NOTE: Upon implementation of Protocol Amendment 5, PK samples for measurement of plasma concentrations of HMPL-689 will not be collected on C3D1 and beyond, and all pharmacodynamic biomarker and pharmacogenetic sample collections will be halted in the dose expansion stage.

Blood samples will be collected at noted time points in the protocol. During the dose escalation stage, the time points for PK blood collection from patients are shown in [Appendix 2](#). During the dose expansion stage, the time points for PK blood collection are shown in [Appendix 3](#).

Time points for pharmacodynamic biomarker collection and pharmacogenetic (PGx) collection are shown in [Appendix 4](#). In this table, the pre-dose PGx blood sample is the only collection for patients in dose escalation and is optional. In the dose expansion, PGx blood samples should be collected in all patients to the extent possible. If, for any reason, the sample is not drawn prior to dosing, it may be taken at any follow-up visit.

After each venous blood sampling, the exact time and dates of blood sampling for PK, pharmacodynamic, and PGx analysis should be recorded on the patient's source documentation and the CRF.

5.9.3 Pharmacokinetic, Pharmacodynamic, and Pharmacogenetic Sample Handling and Shipment

Sample handling instructions will be detailed in the Laboratory Manual.

6 ASSESSMENT OF SAFETY

6.1 Safety Plan

HMPL-689 has not been approved for marketing, and clinical development is ongoing. The safety plan for patients in this study is based on clinical experience with HMPL-689 in completed and ongoing studies. Please refer to the HMPL-689 IB for a complete summary of safety information.

Several measures will be taken to ensure the safety of patients participating in this study. Eligibility criteria have been designed to exclude patients at higher risk for toxicities. Patients will undergo safety monitoring during the study, including assessment of the nature, frequency, and severity of AEs. In addition, guidelines for managing AEs, including criteria for dosage modification and treatment interruption or discontinuation, are provided in Section 5.3.

6.2 Safety Parameters and Definitions

Safety assessments will consist of monitoring and recording protocol-defined AEs and SAEs; measurement of protocol-specified hematologic, clinical chemistry, and urinalysis variables; measurement of protocol-specified vital signs; and other protocol -specified tests that are deemed critical to the safety evaluation of the IP.

Sponsor or sponsor's designee is responsible for reporting the relevant SAEs to the applicable regulatory authorities, and participating investigators, in accordance with ICH guidelines and local regulatory requirements.

6.2.1 Adverse Event

According to the ICH guideline for Good Clinical Practice, an AE is any untoward medical occurrence in a clinical investigation patient administered a pharmaceutical product, regardless of causal attribution. An AE can therefore be any of the following:

- Any unfavorable and unintended sign (including an abnormal laboratory finding), symptom, or disease temporally associated with the use of a medicinal product, whether or not considered related to the medicinal product;
- Any new disease or exacerbation of an existing disease (a worsening in the character, frequency, or severity of a known condition), except as described in Section 6.3.1.8. Recurrence of an intermittent medical condition (e.g., headache) not present at baseline;
- Any deterioration in a laboratory value or other clinical test (e.g., ECG, Xray) that is associated with symptoms or leads to a change in study treatment or concomitant treatment or discontinuation from IP;
- Adverse events that are related to a protocol-mandated intervention, including those that occur prior to assignment of study treatment (e.g., screening invasive procedures such as biopsies).
- Clinical features or clinical sequelae of a suspected overdose of either study drug or a concomitant medication.

6.2.2 Serious Adverse Events

An SAE is any AE that is any of the following:

- Fatal (i.e., the AE actually causes or leads to death);
- Life threatening (i.e., the AE, in the view of the investigator, places the patient at immediate risk of death);
- Requires or prolongs inpatient hospitalization;
- Results in persistent or significant disability/incapacity (i.e., the AE results in substantial disruption of the patient's ability to conduct normal life functions);
- A congenital anomaly/birth defect in a neonate/infant born to a female patient or female partner of a male patient exposed to the IP;
- Considered a significant medical event by the investigator (e.g., may jeopardize the patient or may require medical/surgical intervention to prevent one of the outcomes listed above).

All AEs that do not meet any of the criteria for serious should be regarded as non-serious AEs.

The terms "severe" and "serious" are not synonymous. Severity refers to the intensity of an AE (as in mild, moderate, or severe pain); the event itself may be of relatively minor medical significance (such as severe headache). "Serious" is a regulatory definition and is based on patient or event outcome or action criteria usually associated with events that pose a threat to a patient's life or vital functions. Seriousness (not severity) serves as the guide for defining regulatory reporting obligations.

Severity and seriousness should be independently assessed when recording AEs and SAEs on the CRF.

6.2.3 Protocol-Defined Adverse Events of Special Interest Expedited Adverse Events

- Non-serious AEs of special interest are required to be reported by the investigator to the sponsor immediately (i.e., no more than 24 hours after learning of the event; see Section 6.3.1 for reporting instructions).
- Adverse events of special interest for this study include: Cases of potential drug-induced liver injury (DILI) that include an elevated ALT or AST in combination with either an elevated bilirubin or clinical jaundice, as defined by Hy's law (see Section 6.3.1.5 and Appendix 14), and non-serious cases of interstitial lung disease/pneumonitis (see Section 6.8, Table 6).
- Please refer to the latest IB for additional information.

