4.1.1.2 Definition of Dose Limiting Toxicity

Dose limiting toxicities are defined as the occurrence in the DLT assessment window of any of the following TEAEs, unless equivocally due to underlying malignancy or an extraneous cause:

- a. Non-hematologic toxicity: All non-hematologic TEAEs of Grade 3 or greater with the exception of:
 - i. Grade 3 nausea or vomiting that can be controlled by supportive therapy
- b. Hematologic toxicity:
 - i. Grade 4 neutropenia lasting for more than 5 days
 - ii. Grade 4 thrombocytopenia or Grade 3 thrombocytopenia with bleeding event or requiring platelet transfusion
 - iii. Grade ≥ 3 febrile neutropenia (defined as ANC $< 1000/\text{mm}^3$ with a single temperature $> 38.3^\circ\text{C}$ [101°F] or a sustained temperature of $\geq 38^\circ\text{C}$ [100.4°F] for more than 1 hour)
 - iv. Grade 4 anemia not explained by underlying disease
- c. Any TEAE requiring a dose delay of ≥ 15 days
- d. Any case of Hy's Law

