6.3.1.5 Abnormal Liver Function Test Results

The finding of an elevated ALT or AST in combination with either an elevated total bilirubin ($\geq 2\times$ ULN) or clinical jaundice in the absence of cholestasis or other causes of hyperbilirubinemia is considered to be an indicator of severe liver injury (as defined by Hy’s law). Briefly, Hy’s Law cases have the following three components:

1. The drug causes hepatocellular injury, generally shown by a higher incidence of 3-fold or greater elevations above the ULN of ALT or AST than the (non-hepatotoxic) control drug or placebo;
2. Among trial patients showing such AT elevations, often with ATs $>3\times$ ULN, one or more patients also show elevation of serum TBL to $>2\times$ ULN, without initial findings of cholestasis (elevated serum ALP);
3. No other reason can be found to explain the combination of increased AT and TBL, such as viral hepatitis A, B, or C; preexisting or acute liver disease; or another drug capable of causing the observed injury.

Therefore, investigators must report as an AE in the occurrence of either of the following:

- Treatment-emergent ALT or AST $\geq 3\times$ ULN in combination with total bilirubin $\geq 2\times$ ULN; or
- Treatment-emergent ALT or AST $\geq 3\times$ ULN, in combination with clinical jaundice.

The most appropriate diagnosis or (if a diagnosis cannot be established) the abnormal laboratory values should be recorded on the Adverse Event CRF (see Section 6.3.1.4) and reported to the sponsor’s designee as a non-serious AE of special interest (see Section 6.2.3).

The guidance on diagnosis and management of hepatic AEs (including Hy’s law) can be found in Section 6.8, Table 8.

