	TEAEs leading to death (by PT only)

	Summary scope
	 Any treatment-related TEAE
Treatment-related	- Treatment-related TEAEs with CTCAE grade 3 or higher
TEAE	(maximum CTCAE grade by Grade 5, Grade 4, Grade 3)
	 Treatment-related TEAEs leading to death (by PT only)
Serious TEAE	- All serious TEAE
Serious TEAE	- Treatment-related serious TEAEs

If a subject experienced the same adverse event (as identified by MedDRA preferred term) more than once during the study, the worst occurrence (e.g. worst grade) will be counted. Similarly, if a subject experienced more than one occurrence of the same SOC/PT, the worst occurrence (e.g. worst grade) will be counted within a particular SOC/PT. When summarizing AE by CTCAE grade, if a subject experienced more than one occurrence of the same SOC/PT, the worst severity grade will be counted. Each summary will be ordered by descending order of incidence of SOC and PT within each SOC. If the frequencies of SOC/PT tie, an alphabetic order of SOC/PT will be applied

- Serious adverse events (SAEs) are those adverse events recorded as "Serious" on the "Adverse Events" page of the (e)CRF.
- AEs leading to study medication reduction will be identified as those AEs with a response of "Dose reduced" to the item "Action taken with the study treatment" in the eCRF page of "Adverse Events".
- AEs leading to study medication interruption will be identified as those records with a response of "Drug interrupted" to the item "Action taken with the study treatment" in the eCRF page of "Adverse Events".
- AEs leading to discontinuation of study medication are those AEs with "Drug permanently discontinued" dose action from the eCRF page of "Adverse Events".
- AEs leading to Death are those events which are recorded as "Fatal" in Outcome question/Serious AE related question or Grade 5 in CTCAE grading system on the "Adverse Events" page of the (e)CRF.

AESI SUMMARY

AEs of special interest (AESI) are listed in the below table, and will be identified by MedDRA Query (SMQ):

AESI Category	Search terms	SMQ Code
Hepatic function	MedDRA SMQ "Drug related	20000006 (exclude:
abnormal	normal hepatic disorders - comprehensive	
	search [exclude tumors]" (narrow)	20000012)

MedDRA SMQ "Infective	20000231
pneumonia" (narrow)	
MedDRA SMQ "Noninfectious	20000218
diarrhoea" (narrow+broad)	
MedDRA SMQ "Interstitial lung	20000042
disease" (narrow)	
MedDRA SMQ "Severe cutaneous	20000020
adverse reaction" (narrow)	

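### Protocol Section 6.3.1.5 labels potential Hy's-law liver events non-serious in advance, against the protocol's case-by-case rule, so a case can drop out of the SAE outputs

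*Protocol*

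**What the plan says.** Protocol Section 6.3.1.5 describes raised ALT or AST with raised bilirubin or jaundice, without cholestasis or another cause, as a finding that "is considered to be an indicator of severe liver injury". It makes reporting mandatory when a treatment-emergent ALT or AST reaches 3 × ULN together with total bilirubin of 2 × ULN or clinical jaundice. The event is to go to the sponsor's "designee as a non-serious AE of special interest (see Section 6.2.3"). No clause covers a case that meets a seriousness criterion.

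Section 6.2.3 gives the reporting deadline and the list of AEs of special interest (AESIs). The deadline sentence is "Non-serious AEs of special interest are required to be reported by the investigator to the sponsor immediately", meaning within 24 hours. The hepatic item reads "Cases of potential drug-induced liver injury (DILI) that include an elevated ALT or AST in combination with either an elevated bilirubin or clinical jaundice" and carries no seriousness qualifier. The lung item does carry one: "and non-serious cases of interstitial lung disease/pneumonitis".

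Seriousness is governed elsewhere. Section 6.2.2 lists the criteria, among them "Considered a significant medical event by the investigator", and requires severity and seriousness to be assessed independently. Section 6.2.7 requires a seriousness assessment for each recorded event. Section 6.3.1 has the serious box ticked for any entry that fits the criteria.

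On the analysis side, SAP Section 17.2 states "Serious adverse events (SAEs) are those adverse events recorded as" serious on the adverse-event CRF page.

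**The concern.** An instruction that fixes seriousness in advance conflicts with a rule that seriousness is judged for each event. A site reading 6.3.1.5 alone would leave the serious box blank. A site reading 6.2.2 and 6.3.1 could tick it for the same patient, on the ground of a significant medical event. Both would be following the protocol.

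This matters because SAEs and treatment-related SAEs are named in the Stage 1 primary safety endpoint (Protocol Table 1) and the SAP draws them from that one field. Section 6.2.2 also makes seriousness the guide to regulatory reporting obligations. The event concerned is an important liver signal: among the dose-limiting toxicities, Section 4.1.1.2 lists "Any case of Hy's Law".

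**Working it through.** The plan states no figure on this point, so there is none to reproduce. The check follows one qualifying case through the documents.

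**Step 1. What the site is told.**
- Section 6.3.1.5: report as a non-serious AESI, with no alternative.
- Sections 6.2.2, 6.2.7 and 6.3.1: assess seriousness for each event and tick the box if any criterion is met.

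Both sets apply to the same event, and nothing in the supplied text says which prevails.

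**Step 2. Where the label has an effect.** Suppose the case is filed as 6.3.1.5 instructs.

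| Output or report | What it depends on | Effect of the non-serious label |
|---|---|---|
| Serious and treatment-related serious TEAE tables, SAE listing (SAP 17.2) | Serious field on the CRF | Case absent |
| AESI row for events meeting SAE criteria (SAP 17.2) | Not stated; presumably the same field | Case absent if so |
| Investigator safety reports (Protocol 6.4.2) | Suspected unexpected serious reaction | Not triggered |
| 24-hour report to the sponsor on the SAE form (Protocol 6.4.1) | SAE or AESI, any attribution | None |
| AE listing, hepatic AESI summary (SAP 17.2) | All AEs; preferred term within the SMQ | None |
| DLT table (SAP 17.1) | DLT in the Stage 1 window | None |
| TEAEs leading to discontinuation (SAP 17.2) | Action taken on the CRF | None |
| Liver-test and Hy's-law summary (SAP 17.4) | Laboratory values | None |

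**Step 3. Late cases.** Section 6.2.5 collects all AEs until 30 days after the last dose or the start of new anti-neoplastic therapy, whichever is earlier. After that, only SAEs related to HMPL-689 are reported. SAP 17.2 likewise counts a later event as a TEAE only if it is a treatment-related SAE. A qualifying case that arises after the cut and is regarded as non-serious could go unreported, and it would not be tabulated as a TEAE. For such a case the safeguards in the lower rows of the table cannot be relied on.

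**Step 4. Size.** The amendment summary gives expected enrolment of about 100 patients. One case moves the overall SAE proportion by 1/100 = 1 percentage point. The documents give no expected number of Hy's-law cases.

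**Step 5. The lung item.** Section 6.2.3 restricts this AESI to non-serious cases. SAP 17.2 identifies it by SMQ without regard to seriousness and plans rows for AESIs that are serious or fatal. The two definitions disagree, but nothing is lost: a serious case is still reported within 24 hours as an SAE and is still tabulated through the SMQ.

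**The case against.** The strongest reply is that 6.3.1.5 contains one loose phrase and the rest of the protocol corrects it. Sections 6.2.2, 6.2.7 and 6.3.1 stay in force, and the SAP's planned row for AESIs meeting SAE criteria shows that AESI status and seriousness were meant to be separate. On that view a hospitalised, life-threatening or fatal case would be marked serious anyway, and only the investigator-judged criterion of a significant medical event is exposed. The sponsor also has the details within 24 hours. This stands as a limit on the consequence. It does not remove the contradiction, and the supplied text describes no sponsor step that reassesses seriousness.

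A reader might infer three stronger points that the documents do not support.

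- *That Section 6.2.3 itself classifies Hy's-law cases as non-serious.* Its opening sentence sets a deadline. The hepatic item has no qualifier; only the lung item has one.
- *That these cases must be serious because they are severe, dose-limiting or grounds for permanent discontinuation in Table 8.* None of these is a seriousness criterion in 6.2.2, which separates severe from serious. The groups also differ: 6.3.1.5 is triggered by laboratory values or jaundice, whereas its three-part description of Hy's law and Table 8 add that no other cause is found. SAP 17.1 narrows that gap, because it defines the Hy's-law DLT by raised transaminase and bilirubin collected as an AESI. Even so, DLT status does not settle seriousness.
- *That the cases fall outside regulatory reporting altogether.* Section 6.4 refers to 6.4.2 for non-serious AESIs too, and 6.4.2 states a general sponsor duty to notify regulators about product safety. Only the investigator safety report is tied to serious reactions.

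**Conclusion.** The contradiction in Section 6.3.1.5 is real and should be corrected. Its effect is possible rather than automatic. For on-treatment cases it is confined to the SAE tables and listing and to reporting that depends on seriousness. A late-onset case could go further and not be reported. The number of cases is likely small, at 1 percentage point of the SAE proportion for each case in about 100 patients, and the liver signal is not hidden from the sponsor while patients are on treatment.

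The conclusion assumes that some sites follow 6.3.1.5 literally, and that the supplied text is the whole instruction. Appendix 14, on evaluating possible drug-induced liver injury, is cited but not in the supplied text and may add to it; its absence is not counted against the plan. The lung wording is a secondary mismatch with no demonstrated loss.

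**What to change.** 1. In Protocol 6.3.1.5, replace the instruction to report as a non-serious AESI with: *as an AE of special interest; seriousness is assessed separately under Section 6.2.2*.
2. Before database lock, query the seriousness of each recorded potential Hy's-law AESI. Enrolment has been halted, so this query is what corrects events already on file; the rewording helps only patients still being treated or followed.
3. As a secondary alignment, remove the non-serious qualifier from the ILD/pneumonitis item in Protocol 6.2.3, so that it agrees with the SAP's SMQ definition.

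The cost is two wording edits and one data query, and the SAE count may rise slightly. No dose, stopping rule or patient management changes.
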